**Table 1. General Timeline**

Year 1	Month											
	1	2	3	4	5	6	7	8	9	10	11	12
Clinical Trial Registration 	X											
Purchasing 	X											
Staff Training/Check-in	X			X					X			
Steering Committee meeting	X	X	X	X	X	X	X	X		X	X	X
Enrollment Target 		12	12	12	12	12	12	12	12	12	12	12
Completion Target 			12	12	12	12	12	12	12	12	12	12
Interim data analysis (25% and 50% recruitment)							X				X	
Year 2	Month											
	13	14	15	16	17	18	19	20	21	22	23	24
Staff Training/Check-in	X											
Steering Committee meeting	X	X	X	X	X	X	X	X	X	X	X	X
Enrollment Target 	12	12	12	12	12	12	12					
Completion Target 	12	12	12	12	12	12	12	12				
Data analysis									X	X		
Manuscript preparation; Poster abstract submission										X	X	X
Clinical Trial Registration: Data updates 										X	X	

This study will be registered and maintained at clinicaltrials.gov; Registration will be completed prior to recruiting the first subject.

If grant funding is able to be attained, purchasing outlined in the grant will be completed in month 1 of the award period.

Enrollment and completion targets are estimates based on an 18 month enrollment period. For a 12 month enrollment period, the enrollment and completion targets would be 18 participants per month, with the completion target ending in month 13.

**Participants, Settings, and Inclusion/Exclusion Criteria:** To participate in this study, participants must be recruited at one of the three participating rehabilitation centers: Gaylord Specialty Healthcare (Wallingford, CT), MedStar National Rehabilitation Hospital (Washington, DC), or Spaulding Rehabilitation Hospital Cape Cod (Sandwich, MA).

To be eligible for study participation, subjects must meet the following *Inclusion Criteria*:

- Admitted to one of the listed study locations for inpatient rehabilitation following either

ischemic or hemorrhagic stroke and medically stable for the therapy program.

- Be 18 years of age or older.
- Discharge date of 10 days or longer at study consent
- Have at least a moderate fall risk or better, shown by an admission BBS score of 21/56 or greater.
  - Patients that score below 21 or are non-ambulatory will not be considered for this study.

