  - Patients that are emergently re-admitted to acute care and subsequently re-admitted to the stroke rehabilitation program will be reassessed for appropriateness of continuation in the study on a case by case basis.
  - Patients that progress to a BBS score of 21 or greater during their stay, and have a set discharge date of 10 days or longer, can be approached for study recruitment.
- Appropriate cognition
  - Able to read and understand the consent, in English or a language available by translator services, based on the judgment of the clinical team, either by using outcomes measures, i.e. SLUMS  $\geq$  20, or through clinical evaluations and team discussion. Eligibility will ultimately be decided by the treating physician and/or in combination with the participant's clinical team.
- Ability to tolerate and actively participate in at least 2 and up to 6 study related BWSS therapy sessions.
  - Study related therapy sessions will last a minimum of 15 minutes, up to 30 minutes in the BWSSs.

Those who present with one or more of the following *Exclusion Criteria* will not be eligible for study participation:

- Cognitive deficits that would disrupt the ability to provide informed consent as described above
- Active enteric infection control precautions
  - Subjects would be eligible once precautions are lifted
- Ongoing orthostasis
- Uncontrolled hyper/hypotension
- Active seizures
- Spinal stabilization with the use of Halos
- Unstable skin structures (i.e. skin grafts)
- Chest tubes
- Unstable rib or lower extremity fractures
- Severe osteoporosis
- Subjects where pressure around the abdomen, thighs, groin, or shoulders is contraindicated
- New limb amputations
- Vestibular disorders that may impact balance
- Premorbid conditions that may impact balance
- Patients requiring more than 50% high flow oxygen as consistent with inpatient therapy guidelines
- Subjects who weigh more than 450 pounds, per the structural limitations of the ZeroG system
- Anyone belonging to a vulnerable population as described below, including subjects under the age of 18 and who are or might be pregnant

Equipment and Instruments: Several pieces of equipment and outcome instruments will be needed for this study. The ceiling-track mounted, FDA listed, ZeroG body weight support system

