BWSS (Aretech LLC, Ashburn, VA) and the Training Responses in Postural Rehabilitation (TRiP) balance perturbation module (Aretech LLC, Ashburn, VA) will be the primary pieces of equipment required to complete this study. All study locations already have the ZeroG BWSS and TRiP module installed.

In addition to the equipment, several outcome measurements will be collected throughout the study duration. Balance specific measurements that will be collected include the BBS, an objective balance measure, and the Activities Specific Balance (ABC) scale, a subjective patient reported measure. When appropriate for the patient, an admission BBS is collected within 72 hours of admission at all study locations by the patient's primary therapist. This admission evaluation will be used to initially identify potential subjects with an admitting BBS of 21 or greater; this will be used as the pre-intervention assessment (pre-assessment) during data analysis. When patients are discharged, a follow-up BBS is typically collected at all study locations. However, discharge may not always occur in a timely fashion after the conclusion of the study. To address this, a post-intervention assessment (post-assessment) will be collected within 48 hours of the last study session if not already collected by the participant's primary therapist during that time. The patient reported ABC scale will be collected during the informed consent process and immediately following the last study session.

To evaluate gait, the objective self selected 10 Meter Walk Test (10MWT) assessment will be conducted. If not already conducted during the participant's admission evaluation, a 10MWT pre-assessment will be conducted by site investigators within 48 hours prior to the first study session. A post-assessment 10MWT will be collected within 48 hours of the last study session if not already collected by the participant's primary therapist during that time.

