**Subject identification, recruitment, and pre-assessments:** As described above, qualifying patients will initially be screened/identified through internal reports generated at each study site summarizing admission BBS scores for recently admitted patients. Screening will continue until the target number of participants have completed the study and/or the pre-determined statistical guidelines have been met. After initial screening, the additional inclusion/exclusion criteria will be considered with attending physician approval and the patient approached for consent. After collecting informed consent, participants will be asked to complete an ABC scale pre-assessment. If it was not already conducted by the participant's primary physical therapist at admission, a 10MWT pre-assessment will be conducted within the 48 hours prior to the first treatment session. The admission BBS score will be counted as the participants' BBS pre-assessment. Study procedures and assessments will be conducted according to the general timeline shown in **Table 2**.

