**Table 2. Schedule of Study Procedures and Assessments**

Procedure	Admission	Screening	Pre- Intervention	Treatment Sessions						Post- Intervention
				1	2	3	4	5	6	
BBS	X									X
Report generation	X									
Informed consent		X								
Participant group assignment			X							
Collection of demographic and other secondary information as described below 				X						X
Additional stroke information 				X						X
ABC scale				X						X
10MWT				X						X
BWSS Control Intervention					X	X	X	X	X	X
BWSS-P Intervention					X	X	X	X	X	X
TRiP/Perturbation level recording					X	X	X	X	X	X
System on-time/off-time recording					X	X	X	X	X	X
Data transfer										X

The described information can be collected, as available, any time after the subject has consented to the study, but before de-identified data is transferred to the Lead Site.

**Subject assignment:** Consented subjects will be assigned to either the BWSS Standard Intervention (Control) Group or BWSS with Balance Perturbations (BWSS-P) Intervention Group according to a pre-generated randomized assignment sheet. Each randomized assignment sheet will consist of equal BWSS Control and equal BWSS-P assignments whose order has been randomized using the random list generator at <https://www.random.org/lists/>. Co-Investigators at each site, who will not be delivering the study interventions directly, will be given a unique list with a number of assignments that is in proportion to the number of subjects expected to be recruited at the site; additional assignment lists will be generated if needed. These co-Investigators will be responsible for communicating group assignments to study therapists delivering the intervention, and for ensuring that randomization and treatment order is maintained. It is expected that if the assignment scheme is not maintained for whatever reason, that they will report the incident to the steering committee, described below, and how it was/or still needs to be rectified. No matter group assignment, all consented subjects will be asked to conduct all pre- and post-assessments.

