**BWSS Standard Intervention Control Group:** The BWSS control group will conduct at least 2 and up to 6 study related therapy sessions. Study related therapy sessions will last a minimum of 15 minutes up to 30 minutes. Study sessions will be completed over a 2 to 3 week period as part of the subject's inpatient therapy program. Each session must have an active time of at least 15 minutes in the system to be included, up to 30 minutes for each session. To be as pragmatic and clinically relevant as possible, treatment sessions will be incorporated directly into the participants' normal care. Furthermore, we are allowing participants to complete 2 to 6 sessions as dictated by short or unexpected changes to the discharge planning timeline. During each session, participants will conduct balance exercises, including: marching, side-stepping, retro-ambulation, step-taps, and step-ups. They will also conduct various standard gait exercises, including: ambulation over the ground, going up and down stairs, and performing sit-to-stand transitions. Each of the 2 to 6 study sessions will be part of the subject's normal course of therapy. As this is an active clinical comparison, clinical parameters and progression, other than those described

above, will be determined by the treating therapist (i.e. percent body weight support and use of assistive devices) to ensure success and appropriate challenge to the subject.

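### The BBS baseline is not addressed for patients who qualify after admission; as written, points they gained before recruitment count as pre-to-post BBS change

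*Combined protocol and SAP*

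**What the plan says.** All references are to the combined protocol and SAP.

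- **Participants, Settings, and Inclusion/Exclusion Criteria.** The BBS criterion reads "Have at least a moderate fall risk or better, shown by an admission BBS score of 21/56 or greater". Its sub-points say "Patients that score below 21 or are non-ambulatory will not be considered for this study", and then open a second route: "Patients that progress to a BBS score of 21 or greater during their stay" may be approached if enough of the stay remains.
- **Equipment and Instruments.** "When appropriate for the patient, an admission BBS is collected within 72 hours of admission". This evaluation identifies candidates with an admitting score of at least 21, and "this will be used as the pre-intervention assessment (pre-assessment) during data analysis".
- **Subject identification, recruitment, and pre-assessments.** "The admission BBS score will be counted as the participants' BBS pre-assessment". No separate rule is given for the second route.
- **Table 2 ("Schedule of Study Procedures and Assessments").** The BBS row is marked at admission and post-intervention only.
- **Other baselines.** The ABC scale is completed at consent. The 10MWT is done in the 48 hours before the first session, unless it was done at admission.
- **BWSS Standard Intervention Control Group.** On session count: "we are allowing participants to complete 2 to 6 sessions as dictated by short or unexpected changes to the discharge planning timeline".
- **Data Analysis.** BBS is one of five listed primary outcomes. Pre and post values are compared by 2-way ANOVA, or by a mixed-effects analysis where values are missing. Mean improvement is compared across session counts by 2-way ANOVA, with no outcome named. ANCOVA covariates are not named. Late entry and time from admission to first session are not mentioned.

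**The concern.** A late entrant has, by definition, moved from below 21 to 21 or more before being approached. If the admission score remains the baseline, that rise is recorded as if it belonged to the study period. Two analyses are exposed: the pre-to-post BBS change, and any comparison of BBS improvement by number of sessions. The second is not randomised. If late entrants are more common in some session groups than in others, their earlier gain would look like an effect of session count.

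There is also a gap. The admission BBS is taken only when judged appropriate, so a late entrant may have none, and the rule then supplies no pre-assessment.

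**Working it through.** **The plan's own figure.** The sample size of 214 is not in question. For d = 0.39, two-sided alpha 0.05 and 80% power, the normal approximation gives 104 per arm (208) and the t-test 105 per arm (210), both close to 214. It is used below only as a scale.

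**What follows from the documents alone.** Let b be the admission score (20 or less), q the qualifying score (21 or more) and y the post score. Then

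y - b = (y - q) + (q - b), with q - b at least 21 - b.

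The minimum is 1 point at b = 20, 6 at b = 15, 11 at b = 10 and 21 at b = 0. These are observed points. The documents do not give b.

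**Mean gain (assumed inputs).** Let p be the share of late entrants (10-30%, or 21-64 of 214), g their mean gain before entry (5-10 points) and e the mean gain of early qualifiers between admission and consent (0 or 3 points). None of these is in the documents. Pre-entry points in the mean gain are pg + (1 - p)e. Without late entry they would be e, so late entry adds p(g - e):

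| | Lowest | Highest |
|---|---|---|
| e = 0 | 0.1 x 5 = 0.5 | 0.3 x 10 = 3.0 |
| e = 3 | 0.1 x 2 = 0.2 | 0.3 x 7 = 2.1 |

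At an assumed share of 1%, even g = 10 with e = 0 adds only 0.01 x 10 = 0.1.

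**By number of sessions (assumed shares of 30% and 10% in two session groups).** The false difference is (0.3g + 0.7e) - (0.1g + 0.9e) = 0.2(g - e). That is 1.0-2.0 points at e = 0 and 0.4-1.4 at e = 3. The sign reverses if the shares are swapped, and the difference is zero if they are equal.

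**Effect of re-basing late entrants only.** The term in g goes and the early qualifiers' term stays: 0.7e - 0.9e = -0.2e. At g = 5 and e = 3 the false difference changes from 0.4 to -0.6. It becomes larger in size whenever e exceeds g/2. Without late entrants it is zero, provided e is similar across session groups.

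**Missing admission BBS.** The mixed-effects pre/post analysis could keep such a participant. A complete-case analysis of change could not.

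**The case against.** The strongest reply is that this is an omission, not a deliberate rule. The instruments section ties the admission BBS to patients who already score 21 or more, and neither baseline statement mentions the second route. That is fair, and it is why the point is worded as a case not addressed. But the baseline sentence carries no qualification and Table 2 offers no other score, so an analyst following the text would use the admission BBS.

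Second, within-arm gain already includes usual care, and session count is already confounded by discharge timing. Both are true and limit the importance of the point. They do not make the baseline right.

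Third, apart from 21 - b, every figure for size is assumed, and the required remaining stay may make late entry uncommon. This also stands.

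Fourth, re-basing only late entrants leaves early qualifiers' pre-consent gain in place and can worsen the session comparison. This stands too and shapes the fix.

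A reader might infer more than the documents support:

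- *That the treatment comparison is biased.* Entry and the admission score precede assignment, so the extra gain is balanced between arms in expectation.
- *That power is lost.* The pilot d of 0.39 may already contain this variance, so no loss is shown.
- *That a false dose-response in a known direction is shown.* The session analysis names no outcome, and nothing shows which session groups hold more late entrants.
- *That the eligibility text contradicts itself outright.* The two sentences are sub-points of one criterion and can be read as a rule and its exception.

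**Conclusion.** The point holds and is minor. As written, each late entrant with an admission score b contributes at least 21 - b observed pre-recruitment points to BBS change; this needs no assumption beyond the eligibility threshold. The within-arm BBS gain is inflated to a degree that depends on the unreported share of late entrants: 0.5-3.0 points under the assumed ranges with no early gain, 0.2-2.1 with an early gain of 3, and close to nothing if late entry is rare. A session comparison run on BBS improvement is exposed only if that share differs between session groups. The randomised contrast is not biased in expectation.

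**What to change.** 1. In Equipment and Instruments, in the recruitment section and in the BBS row of Table 2, state: *For participants recruited because their BBS rose to 21 or more after admission, the BBS pre-assessment is the qualifying BBS; for all others it is the admission BBS.*
2. Record the date of the baseline BBS, the date of the first session and a late-entry flag.
3. Repeat the pre/post BBS analysis, and any by-session analysis of BBS improvement, without late entrants. Rely on that version for the session comparison. State which outcomes the session analysis covers.
4. If data have already been analysed, as the past tense of the Data Analysis section suggests, label the re-based analysis post hoc and report it beside the admission-BBS analysis.
5. Word the late-entry sentence as an explicit exception to the sentence excluding scores below 21.

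**Cost.** Wording, two dates, one flag and repeat analyses. No new assessment is needed, because the qualifying score must exist before a late entrant can be approached. The drawbacks are that baseline falls on differing days after admission, that a score selected for crossing a threshold carries some regression to the mean, and that early qualifiers keep any gain before consent. At shares of 10-30%, the analysis without late entrants uses 150-193 of 214 participants (214 x 0.7 to 214 x 0.9). For the same SD, the standard error of a mean gain is then about 5-20% larger (1/sqrt(0.9) = 1.05; 1/sqrt(0.7) = 1.20).

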**Table 2. Schedule of Study Procedures and Assessments**

Procedure	Admission	Screening	Pre- Intervention	Treatment Sessions						Post- Intervention
				1	2	3	4	5	6	
BBS	X									X
Report generation	X									
Informed consent		X								
Participant group assignment			X							
Collection of demographic and other secondary information as described below 				X						X
Additional stroke information 				X						X
ABC scale				X						X
10MWT				X						X
BWSS Control Intervention					X	X	X	X	X	X
BWSS-P Intervention					X	X	X	X	X	X
TRiP/Perturbation level recording					X	X	X	X	X	X
System on-time/off-time recording					X	X	X	X	X	X
Data transfer										X

The described information can be collected, as available, any time after the subject has consented to the study, but before de-identified data is transferred to the Lead Site.

**Subject assignment:** Consented subjects will be assigned to either the BWSS Standard Intervention (Control) Group or BWSS with Balance Perturbations (BWSS-P) Intervention Group according to a pre-generated randomized assignment sheet. Each randomized assignment sheet will consist of equal BWSS Control and equal BWSS-P assignments whose order has been randomized using the random list generator at <https://www.random.org/lists/>. Co-Investigators at each site, who will not be delivering the study interventions directly, will be given a unique list with a number of assignments that is in proportion to the number of subjects expected to be recruited at the site; additional assignment lists will be generated if needed. These co-Investigators will be responsible for communicating group assignments to study therapists delivering the intervention, and for ensuring that randomization and treatment order is maintained. It is expected that if the assignment scheme is not maintained for whatever reason, that they will report the incident to the steering committee, described below, and how it was/or still needs to be rectified. No matter group assignment, all consented subjects will be asked to conduct all pre- and post-assessments.

**BWSS Standard Intervention Control Group:** The BWSS control group will conduct at least 2 and up to 6 study related therapy sessions. Study related therapy sessions will last a minimum of 15 minutes up to 30 minutes. Study sessions will be completed over a 2 to 3 week period as part of the subject's inpatient therapy program. Each session must have an active time of at least 15 minutes in the system to be included, up to 30 minutes for each session. To be as pragmatic and clinically relevant as possible, treatment sessions will be incorporated directly into the participants' normal care. Furthermore, we are allowing participants to complete 2 to 6 sessions as dictated by short or unexpected changes to the discharge planning timeline. During each session, participants will conduct balance exercises, including: marching, side-stepping, retro-ambulation, step-taps, and step-ups. They will also conduct various standard gait exercises, including: ambulation over the ground, going up and down stairs, and performing sit-to-stand transitions. Each of the 2 to 6 study sessions will be part of the subject's normal course of therapy. As this is an active clinical comparison, clinical parameters and progression, other than those described

above, will be determined by the treating therapist (i.e. percent body weight support and use of assistive devices) to ensure success and appropriate challenge to the subject.

**BWSS-P Intervention Group:** The BWSS-P intervention group will also conduct 2 to 6 study sessions over a two-week period. Each session must have an active time of at least 15 minutes in the system, up to 30 minutes for each session. Participants in the BWSS-P group will conduct the same balance and gait exercises as the control group, however, these sessions will include eight perturbations, two in each direction (lateral left, lateral right, anterior, and posterior). Perturbations will occur while static/standing (lateral, anterior, posterior) and dynamically while ambulating (anterior, posterior). Each of the 2 to 6 study sessions will be part of the subject's normal course of therapy. As this is an active clinical comparison, clinical parameters and progression, other than those described above, will be determined by the treating therapist (i.e. percent body weight support and use of assistive devices) to ensure success and appropriate challenge to the subject. The TRiP or perturbation level will be progressed to the point of loss of balance, or very near loss, without recovery. The perturbation level should then be then decreased by one level for treatment. All 8 perturbations will occur at this level until it is clinically appropriate to progress again. The intensity of TRiP perturbation ranges from level 1 to 10, minimal to maximum, respectively.

**Post-Assessments:** After the completion of the subjects' final BWSS session before discharge, investigators will conduct an ABC and 10MWT post-assessment no longer than 48 hours following the final session. Follow-up BBS are often completed prior to discharge as part of patient/participant's standard of care. However, in the case that there is an unexpected delay or there is a significant length of time until the participant's discharge, a post-assessment BBS will be conducted no longer than 48 hours following the last session.

**Data Analysis:** Data were analyzed using GraphPad Prism (version 10; GraphPad Software, Boston, MA) and RStudio (version 4.2.2, Posit Software, PBC, Boston, MA] using the *car* package.

Descriptive data is reported as mean (95% confidence interval). If hypothesis testing was done, data were reported with a p-value, and significance was set at  $\alpha=.05$ . The primary outcome measures used in our analyses were the BBS, ABC, 10MWT, CMS GG0130 Mobility scores, and CMS GG0170 Self-care scores. Data were determined to be missing completely at random and were dealt with via complete case analysis and mixed-effects analysis as applicable. Data were also assessed for violations in assumptions of their given tests, and were dealt with via non-parametric analysis as necessary.

Categorical data was analyzed using Chi-square testing. Unpaired t-tests or Mann-Whitney U tests were utilized as necessary to evaluate between-group differences in continuous outcome variables.

Analysis of covariance (ANCOVA) was used to account for between group differences while controlling for covariates. To evaluate if there were differences between pre- and post-intervention data, a 2-way analysis of variance (ANOVA) was utilized, with mixed-effects analysis being utilized when data was missing. Differences in average improvement by number of sessions completed were evaluated using a 2-way ANOVA. Differences in outcome measure between testing sites were analyzed using one-way ANOVA or Kruskal-Wallis testing. Multiple comparisons were analyzed using, Fisher's, Dunn's, Tukey's multiple comparison tests as appropriate.

References:

2. Parametric ANCOVA and the Rank Transform ANCOVA When the Data are Conditionally Non-Normal and Heteroscedastic - Stephen F. Olejnik, James Algina, 1984 [Internet]. [cited 2024 Apr 4]. Available from: <https://journals.sagepub.com/doi/10.3102/10769986009002129>

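### Each site's full assignment list goes to site co-investigators and no concealment procedure is described, so allocation concealment is not assured

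*Combined protocol and SAP*

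**What the plan says.** Under Subject assignment, participants are allocated "according to a pre-generated randomized assignment sheet". On the structure of a sheet the plan says: "Each randomized assignment sheet will consist of equal BWSS Control and equal BWSS-P assignments". The order comes from an online list randomiser.

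On custody, "Co-Investigators at each site, who will not be delivering the study interventions directly, will be given a unique list", and this list comes "with a number of assignments that is in proportion to the number of subjects expected to be recruited at the site". The same people are "responsible for communicating group assignments to study therapists delivering the intervention, and for ensuring that randomization and treatment order is maintained". They report any departure from the scheme to the steering committee. Assignment comes after consent: "Consented subjects will be assigned to either the BWSS Standard Intervention (Control) Group" or to the perturbation group.

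The section on subject identification and recruitment describes screening from site reports of admission Berg Balance Scale (BBS) scores, then approval by the attending physician, then the approach for consent. It does not name who approaches the patient or takes consent. On the cognition criterion, the inclusion list says: "Eligibility will ultimately be decided by the treating physician and/or in combination with the" clinical team. Section 1.1 states that participants, investigators and the assessor cannot be masked.

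**The concern.** Concealment means that whoever influences entry to the trial cannot know the next assignment until the patient is irrevocably in. The plan separates the list holder from treatment delivery, which is a different function. It sets no separation from recruitment.

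If the next assignment is known, the choice of whom to approach, and when, can come to depend on the arm. The groups then differ in prognosis at entry. Covariate adjustment removes only the part of that difference carried by measured covariates.

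This matters more here because the trial is fully open. Masking after assignment is ruled out, but concealment before assignment remains feasible in an open-label trial and is one of the few protections left.

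**Working it through.** **1. Does any stated step conceal the sequence?**

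- *Separation from delivery* (Subject assignment). This keeps the list holder from being the treating therapist. It says nothing about screening, eligibility, approach or consent.
- *Assignment after consent* (Subject assignment). This fixes when a participant is formally assigned. The holder of an open list knows the next assignment before that.
- *Reporting of departures* (Subject assignment). This covers breaks in the sequence and is done by the list holders themselves. Selective approach leaves the sequence intact, so it would trigger no report.

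No other section adds a safeguard.

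**2. Is there room for foreknowledge to act?**

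Some entry conditions are numeric, such as age and a BBS of at least 21. Others need judgement: cognition assessed by the clinical team, ability to tolerate the sessions, and vestibular or premorbid conditions that might affect balance. Timing is also flexible, because patients who reach the BBS threshold during their stay may be approached then.

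**3. How much does an open list reveal?**

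The holder of an open list knows 100% of upcoming assignments. For comparison, suppose a balanced list of 2m assignments were concealed and only past assignments were known. The best-guess strategy (Blackwell-Hodges) then expects this many correct guesses:

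m + 0.5 × (2^(2m) / C(2m, m) − 1)

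List lengths are not given, so these are assumptions:

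| Assumed list length | Expected correct | Share correct |
|---|---|---|
| 20 | 12.34 | 62% |
| 72 (about 214/3) | 40.84 | 57% |
| 108 | 60.03 | 56% |

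Concealment would bring predictability close to chance.

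**4. The plan's sample size, as background**

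Inputs from section 1.1: d = 0.39, two-sided α = 0.05, power 80%, total 214.

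- Normal formula: n per arm = 2 × ((1.960 + 0.842) / 0.39)² = 103.2, so 104 per arm and 208 in total.
- The t-based calculation gives 105 per arm, 210 in total.
- An unrounded d of 0.385 to 0.386 gives 214 exactly.

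The stated figure is consistent with its inputs. With equal allocation it means 214 / 2 = 107 per arm. Concealment does not change it.

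**5. What would a shift in prognosis do?**

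The shift b is an assumption; no document gives one. There is no treatment effect, and the test is an unadjusted two-sample test with 107 per arm.

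SE of the difference in SD units = √(2/107) = 0.1367.

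False-positive rate ≈ Φ(b/SE − 1.960) + Φ(−b/SE − 1.960).

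| Shift b (SD) | b/SE | False-positive rate | b as share of 0.39 |
|---|---|---|---|
| 0.05 | 0.37 | 6.5% | 13% |
| 0.10 | 0.73 | 11.3% | 26% |
| 0.20 | 1.46 | 31.0% | 51% |

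The noncentral t gives 11.3% at 0.10 SD and 30.8% at 0.20 SD, so the range is about 11% to 31% either way.

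**The case against.** A reader might infer that the staff who screen, consent and assess are the ones holding the list. The documents do not say so. Physicians and the clinical team decide on cognition, the attending physician approves entry, and the person taking consent is unnamed. None of them is described as seeing the sheet, so advance knowledge is established only for the list holder. This objection stands. It limits the point to an absence of protection; it does not supply the protection.

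A reader might also bring in outcome assessment, since "a 10MWT pre-assessment will be conducted by site investigators within 48 hours prior to the first study session" when the walk test (10MWT) was not done at admission. That sentence does not identify those investigators as list holders. An assessor's knowledge of the arm is a masking matter, which section 1.1 already concedes, so it is not part of this point.

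Selection is also partly constrained. The first screen is a numeric BBS threshold. By the main admission route, that score is taken by the primary therapist within 72 hours of admission and serves as the BBS baseline. This narrows the scope for steering but leaves the choice and timing of approach open.

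Finally, the Data Analysis section lists ANCOVA, with covariates unnamed. It would remove whatever part of a shift those covariates carry. The false-positive rates above are therefore unadjusted and hypothetical. They are not a forecast.

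**Conclusion.** The point holds as a gap in protection. A person at each site holds the complete order, no concealment step is described, and list holders' roles in recruitment are unrestricted. The documents do not show that selection occurred or that list holders recruit.

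The size of any bias is unknown. The range of about 11% to 31% rests on an assumed prognosis shift of 0.1 to 0.2 SD, 107 per arm and no covariate adjustment; a shift of 0.05 SD would give 6.5%. The change is cheap and worth making, and the sample size is unaffected.

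**What to change.** Keep all lists at the Lead Site, which already receives the sites' de-identified data, and out of sight of site staff. Release one assignment at a time, by email or database form, only after consent, eligibility and baseline assessments have been logged, and record the release time. Baseline should be included because the walk-test window is tied to the first session and not to assignment. An alternative is sequentially numbered, sealed, opaque envelopes prepared by the Lead Site.

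As a minimum, add a sentence barring list holders from screening, eligibility decisions, approaching patients and taking consent. This is a partial remedy, because the sequence would still be open at the site.

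The cost is protocol wording, a short release step per participant and a small delay between consent and assignment.

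The design sections use the future tense but the Data Analysis section uses the past tense, so enrolment may already be over. In that case, report who held the lists and what part they played in enrolment, and state the limitation.
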